As the EPO guidelines only provide guidance for EPO use: EPO dosing, dose adjustments and dose discontinuation, and do not specify any criteria for the evaluation of erythroid response in MDS patients, in this study, the assessment of the erythroid response at 12 weeks is performed based on the IWG-2006 criteria ([Appendix 2](#)), which is more widely recognized and used to assess hematologic improvement in anemic patients. An increase in Hb of 1.5 g/dL or more is required for a response. For the assessment of erythroid response, only the hemoglobin component is used and not the reduction of RBC transfusions. As the study population in this trial consists only of patients with low- and Int-1-risk MDS, which receive only few or no transfusions, these patients would otherwise wrongly counted as responders.

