	Hb increased < 1 g/dL from baseline and Hb < 12 g/dL	Increase EPO to 60,000 units/week *
	Hb increase is ≥ 1 g/dL and Hb < 12 g/dL	Continue EPO 40,000 units/week *
	Hb increase is ≥ 1 g/dL and Hb ≥ 12 g/dL	Hold EPO treatment *
Week 12	Hemoglobin status	Action
	Hb increased < 1 g/dL from baseline and Hb < 12 g/dL	If patient is in the combination arm: Discontinue from the study or If patient is in the EPO monotherapy arm: Switch to the combination EPO + DFX
	Hb increase is ≥ 1 g/dL and Hb < 12 g/dL	Continue current EPO dose *
	Hb increase is ≥ 1 g/dL and Hb ≥ 12 g/dL	Hold EPO treatment *

* Patients in combination arm will continue DFX DT 10 mg/kg/day or DFX FCT 7 mg/kg/day treatment

[figure not shown]
The primary objective (erythroid response according to IWG criteria: Hb increase ≥ 1.5 g/dL) will be assessed at 12 weeks of treatment. At any time, if Hb ≥ 12 g/dL, EPO will be stopped until the end of study.

At 24 weeks, patients initially assigned to the combination therapy who showed Hb increase ≥ 1 g/dL at week 12 will be assessed for full hematological response according IWG criteria (Erythroid response: Hb increase from baseline ≥ 1.5 g/dL; Neutrophil response: increase from baseline of ≥ 100% and > 0.5 x 10⁹/L; Platelet response: increase from baseline of ≥ 30 x 10⁹/L). Patients initially treated with EPO alone and switched to the combination therapy with EPO and DFX after 12 weeks will be assessed for erythroid response according to IWG criteria after 24 weeks.

No RBC transfusions are allowed after randomization, as transfusions would affect the endpoints of the trial. Patients who are RBC transfusion dependent must not be enrolled in the study. RBC transfusion dependence is defined as more than 2 units RBC /4 weeks at any time during the last 12 week period prior to study entry (Gale 2011). Patients must be withdrawn from the study anytime when transfusion as rescue therapy is needed.

Safety assessments are routinely performed including collection of AEs, SAEs, vital signs, physical examination, ECG, hematological and biochemistry assessments.

Patients will continue therapy until disease progression or intolerable toxicity, patient decision or death, after 12 weeks of combination treatment without response or after 24 weeks treatment duration at which point an End of Treatment (EOT) Visit will be performed and the End of Treatment CRF page will be completed.

30 day follow-up

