7.1.3 End of Treatment Visit including study completion and premature withdrawal

At the time patients discontinue study treatment, a visit should be scheduled as soon as possible, at which time all of the assessments listed for the End of Treatment (EOT) Visit will be performed. An End of Treatment CRF page must be completed, giving the date and reason for stopping the study treatment.

At a minimum, all patients who discontinue study treatment, including those who refuse to return for a final visit, will be contacted for safety evaluations during the 30 days following the last dose of study treatment.

Patients who discontinue study treatment should be considered withdrawn from the study after the final visit assessments are performed or when it is clear that the patient will not return for these assessments.

If a study withdrawal occurs, or if the patient fails to return for visits, the investigator must determine the primary reason for a patient's premature withdrawal from the study and record this information on the End of Treatment CRF page.

The Investigator must contact the IWR to register the subject's discontinuation.

For criteria for premature withdrawal see [Section 7.1.3.1](#).

[figure not shown]

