7.1.3.1 Criteria for premature patient withdrawal

Patients may voluntarily withdraw from the study or be dropped from it at the discretion of the investigator at any time.

Premature patient withdrawal refers to the point/time when the patient exits from the study prior to the planned completion of all study treatment administration and/or assessments; at this time, all study drug treatment is discontinued and no further assessments are planned.

Patients who become pregnant, withdrew consent, or died must be withdrawn from the study.

Patients may be withdrawn from the study if any of the following occur:

- Unwillingness to comply with procedures as outlined in the study protocol, including unwillingness to comply with the prescribed study treatment
- Discovery of failure of randomization
- Discovery of patient ineligibility
- Intake of prohibited medications
- Adverse event(s)
- Abnormal lab value(s)
- Unsatisfactory therapeutic effect
- Protocol violation
- Lost to follow-up
- Administrative problems

Patients must be withdrawn from the study anytime when transfusion as rescue therapy is needed to ensure that all medically indicated transfusion requirements are covered, regardless of participation in the study.

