10.4.2 Statistical hypothesis, model, and method of analysis

[figure not shown]
A patient is defined as an erythroid responder if the criterion of Hb increase from baseline ≥ 1.5 g/dL is met at any time within the first 12 weeks period. Baseline is defined as the last available Hb value available within windows of 4 weeks prior to or on treatment start date. No imputation will be performed for missing laboratory data.

Difference in proportions between treatment groups with its 95% Agresti-Caffo ([Agresti-Caffo 2000](#)) confidence interval will be provided. Erythroid response proportion will be also summarized by treatment group with its 95% Clopper-Pearson confidence intervals. Analysis will be performed on FAS and PP set.

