14.1 Appendix 1: WHO classification of primary MDS

Table 14-1 WHO classification of primary MDS

Category	Peripheral blood	Bone marrow
Refractory cytopenia with unilineage dysplasia (RCUD)		
RA	Anemia Blasts <1%	Blasts <5% unilineage erythroid dysplasia (in ≥10% of cells)
RN	Neutropenia Blasts <1%	Blasts <5% unilineage granulocytic dysplasia
RT	Thrombocytopenia Blasts <1%	Blasts <5% unilineage megakaryocytic dysplasia
RARS	Anemia No Blasts	Blasts <5% ringed sideroblasts ≥15% unilineage erythroid dysplasia
RCMD	Cytopenia(s) Blasts <1% no Auer rods	multilineage dysplasia ± ring sideroblasts Blasts <5% no Auer rods
RAEB-I	Cytopenia(s) Blasts <5% no Auer rods	unilineage or multilineage dysplasia Blasts 5%–9% no Auer rods
RAEB-II	Cytopenia(s) Blasts 5%–19% ± Auer rods	unilineage or multilineage dysplasia Blasts 10%–19% ± Auer rods
MDS del (5q)	Anemia Blasts <1%	del(5q) deletion Blasts <5% hypolobated megakaryocytes
Childhood MDS, including refractory cytopenia of childhood (RCC)	pancytopenia	<5% marrow blasts for RCC, hypocellular marrow
MDS–U	Cytopenias Blasts ≤1% no Auer rods	does not fit any other category dysplasia or MDS-associated karyotype Blasts <5% no Auer rods

14.2 Appendix 2: Modified International Working Group response criteria for hematologic improvement

Table 14-2 Modified International Working Group response criteria for hematologic improvement

Category	Pretreatment	Modified IWG Response Criteria (≥ 8 weeks)
Erythroid response	Hb < 11 g/dL	Hb increase by ≥ 1.5 g/dL Reduction of ≥ 4 RBC transfusions/8 weeks versus pretreatment requirements in previous 8 weeks; only RBC transfusions given for a pretreatment Hb of ≤ 9.0 g/dL count
Platelet response	< 100 x 10 ⁹ /L	increase of ≥ 30 x 10 ⁹ /L (starting with > 20 x 10 ⁹ /L) Increase from < 20 x 10 ⁹ /L to > 20 x 10 ⁹ /L by ≥100%
Neutrophil response	< 1.0 x 10 ⁹ /L	increase of ≥ 100% and > 0.5 x 10 ⁹ /L
Progression/ relapse after hematological improvement		≥ 1 of the following: ≥ 50% decrement from maximum response levels in granulocytes or platelets; reduction in Hb by ≥1.5 g/dL; transfusion dependence

See [Cheson 2006](#).

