2.9.1.2 Statistical hypothesis, model, and method of analysis

A patient is defined as an erythroid responder if the criterion of Hb increase from baseline ≥ 1.5 g/dL is met at any time within the first 12 weeks period.

Baseline is defined as the last available value within windows of 4 weeks prior to or on treatment start date. No imputation will be performed for missing Hb value.

Difference in proportions between treatment groups with its 95% Agresti-Caffo (Agresti-Caffo 2000) confidence interval will be provided. Erythroid response proportion will be also summarized by treatment group with its 95% Clopper-Pearson confidence intervals (Clopper and Pearson 1934). Analysis will be performed on FAS.

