S21	Epo dose reduced below assigned dose as per protocol for more than 1 week in period week 1-12	Report as PD, include in FAS and Safety Set.
S22	Epo dose reduced below assigned dose as per protocol for more than 1 week in period week 13-24	Report as PD, include in FAS and Safety Set.
S23	Epo dose increased above assigned dose as per protocol for more than 1 week in period week 1-12	Report as PD, include in FAS and Safety Set.
S24	Epo dose increased above assigned dose as per protocol for more than 1 week in period week 13-24	Report as PD, include in FAS and Safety Set
S03	Epo dose maintained at 40.000 units/week and not increased to 60.000 units/week after 4 weeks as per protocol for more than 1 week but Hb increase < 1 g/dL and total Hb < 12 g/dL	Report as PD, include in FAS and Safety Set.
S05	Epo dose increased to 60.000 units/week and not maintained at 40.000 units/week after 4 weeks as per protocol for more than 1 week but Hb increase ≥ 1 g/dL and total Hb < 12 g/dL	Report as PD, include in FAS and Safety Set.
S06	Patient randomized to monotherapy not switched to combination therapy as per protocol or switch delayed for more than 1 week after 12 weeks of treatment but Hb increase < 1 g/dL and total Hb < 12 g/dL	Report as PD, include in FAS and Safety Set.
D12	Patient randomized to combination therapy not discontinued after 12 weeks of treatment as per protocol or discontinuation delayed for more than 1 week but Hb increase < 1 g/dL and total Hb < 12 g/dL	Report as PD, include in FAS and Safety Set.
S10	Patient randomized to combination therapy stopped DFX treatment for more than 1 week in period week 1-12 not as per protocol	Report as PD, include in FAS and Safety Set.
S25	Patient assigned to combination therapy stopped DFX treatment for more than 1 week in period week 13-24 not as per protocol	Reported as PD, include in FAS and Safety Set.
M01	Forbidden concomitant medication as per	Report as PD,

	protocol	include in FAS and Safety Set.
M02	Patient received iron chelation therapy other than the study treatment	Report as PD, include in FAS and Safety Set.
D01	Transfusion during the study but not withdrawn	Report as PD, include in FAS and Safety Set.
D02	Pregnancy during the study, but not withdrawn	Report as PD, include in FAS and Safety Set.
S11	Patient randomized but received wrong study drug	Report as PD, include in FAS and Safety Set.

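### The primary responder rule has no transfusion condition, so a transfused patient kept in the FAS can be counted as an erythroid responder on a post-transfusion Hb

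*SAP*

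**What the plan says.** **Response rule.** SAP 2.9.1.2: "A patient is defined as an erythroid responder if the criterion of Hb increase from baseline ≥ 1.5 g/dL is met at any time" in the first 12 weeks. Protocol 10.4.2 has the same rule: the criterion "is met at any time within the first 12 weeks period". Neither mentions transfusion. The instruction not to impute covers missing Hb only. Protocol 6.1.4 also treats patients whose Hb reaches 12 g/dL as responders, again without a transfusion condition.

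**Relation to the IWG criteria.** Protocol 2.3 explains that "only the hemoglobin component is used and not the reduction of RBC transfusions". Table 14-2 in Protocol Appendix 2 heads the IWG response criteria with a minimum of 8 weeks; the study rule does not require a sustained rise.

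**Conduct rules.** Protocol 4.1: "No RBC transfusions are allowed after randomization, as transfusions would affect the endpoints of the trial". Protocol 7.1.3.1: "Patients must be withdrawn from the study anytime when transfusion as rescue therapy is needed".

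**When the conduct rules fail.** SAP Table 4-7 lists deviation D01, "Transfusion during the study but not withdrawn". The action is to report it and keep the patient in the FAS and Safety Set. SAP 2.9.1.2 analyses the primary endpoint on the FAS only, whereas Protocol 10.4.2 specified the FAS and the per-protocol set.

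**Exit sample.** On stopping treatment, Protocol 7.1.3 asks for a visit as soon as possible at which "all of the assessments listed for the End of Treatment (EOT) Visit will be performed". Table 7-1 includes hematology at that visit, and Protocol 4.3 allows up to 2 weeks after the drug is stopped.

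**The concern.** The protocol recognises that a transfusion distorts the endpoint, but it protects the endpoint only through conduct: do not transfuse, and withdraw the patient if a transfusion is needed. The SAP foresees that this can fail and does not say which of that patient's Hb values may then count. Read literally, the rule lets a transfused patient qualify on a single post-transfusion value.

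The error would be of an awkward kind: a patient rescued because treatment was not holding Hb would be recorded as a treatment success. Treatment is open label, so decisions to transfuse or to keep a patient on study are made with the arm known, and cases need not be balanced between arms.

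**Working it through.** **Does anything in the text block the count?**

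1. *Transfused, not withdrawn (D01).* The patient stays in the FAS and keeps attending. Hematology up to week 12 is drawn at Visits 5, 7, 8 (only if EPO was increased), 9 and 10. No passage excludes a post-transfusion value at these visits. D01 is tabulated and listed under SAP 2.4, but that does not alter the responder count.
2. *Withdrawn for transfusion.* The exit sample may come after the transfusion. Whether it counts is undetermined: SAP 4.2.11 gives the End of Treatment visit a window of Day 161 to 175 only and says nothing about an earlier one. If values are assigned by study day, it counts; on a strict reading of the window, it may be dropped. This route is therefore conditional.
3. *Protocol 2.3* stops a fall in transfusion need from counting as response. It does not address Hb measured after a transfusion.

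**How large a rise is needed?** The Amendment 1 rationale describes 8 g/dL as a level below which transfusion is indicated in most countries. It explains an entry criterion and is used here only as a reference point. From 8 g/dL, the rise needed = baseline + 1.5 - 8.

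| Baseline (g/dL) | Rise needed (g/dL) |
|---|---|
| 7.6 (8 less 5% entry tolerance) | 1.1 |
| 8.0 | 1.5 |
| 9.0 | 2.5 |
| 10.0 | 3.5 |
| 10.5 (10 plus 5% entry tolerance) | 4.0 |

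The first row implies that Hb had risen on treatment before the transfusion. A patient transfused at or below baseline needs 1.5 g/dL plus whatever Hb had fallen.

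**The plan's own interval.** Protocol 10.8 and SAP 2.11 give (-0.04, 0.44) for a 20-point difference from a 40% reference rate with 60 patients. This reproduces only if 60% and 40% are entered as already adjusted proportions with denominators of 32: 0.20 ± 1.96 × √[(0.6×0.4 + 0.4×0.6)/32] = 0.20 ± 0.240. The standard Agresti-Caffo formula is used below.

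**Effect of false responders.** Inputs: 60 patients, 1:1, so 30 per arm; true result assumed to be 18/30 (combination) v 12/30 (EPO), which are the plan's 60% and 40%. Adjusted proportion p = (x+1)/(n+2); interval = (p1 - p2) ± 1.96 × √[p1(1-p1)/32 + p2(1-p2)/32].

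For 18 v 12: p1 = 19/32 = 0.594 and p2 = 13/32 = 0.406, so the adjusted difference is 0.1875, with limits -0.053 and 0.428.

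| False responders | Counts | Raw difference (points) | 95% interval |
|---|---|---|---|
| None | 18 v 12 | 20.0 | -0.053 to 0.428 |
| 1 in EPO arm | 18 v 13 | 16.7 | -0.086 to 0.398 |
| 2 in EPO arm | 18 v 14 | 13.3 | -0.118 to 0.368 |
| 1 in combination arm | 19 v 12 | 23.3 | -0.020 to 0.458 |
| 2 in combination arm | 20 v 12 | 26.7 | 0.013 to 0.487 |
| 1 in each arm | 19 v 13 | 20.0 | -0.053 to 0.428 |

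Each case adds 1/30 = 3.3 points to its arm. One case in each arm leaves the difference unchanged but raises the rates from 60.0% and 40.0% to 63.3% and 43.3%. The Clopper-Pearson interval for the EPO arm moves from 22.7-59.4% to 25.5-62.6%.

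**The case against.** The strongest reply is that the design already deals with this. Transfusion is banned and withdrawal is mandatory, so the main route needs a prohibited transfusion, a failure to withdraw, a later scheduled Hb within 12 weeks, and a value at least 1.5 g/dL above baseline rather than above the pre-transfusion low. Deviations are listed, so in about 60 patients any such case could be found and the rate recomputed. RAP Module 8, not among the documents, holds derivations and some exclusion flags and may already contain a rule. The protocol's per-protocol analysis could remove such a patient if D01 is classed as a major deviation. Finally, barring every later Hb penalises a patient transfused early for an unrelated reason, such as bleeding, who later has a genuine rise; a limited exclusion window could be defended instead.

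Much of this limits frequency, and that stands: cases will be few and may be none. It does not change what the stated rule counts. Recomputing after the fact would be a post-hoc decision by a team that SAP 3.3 describes as unblinded. The per-protocol analysis is absent from the SAP's analysis sets and would leave the FAS result as it is. The SAP text does not say that Module 8 covers transfusion, and a primary endpoint definition should be readable where the endpoint is defined. On the exclusion window, barring all later Hb matches the protocol, under which a compliant patient would have left the study at the transfusion. The loss of an occasional late genuine response is a real but small cost.

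**Conclusion.** The concern holds. Applied as written, the primary rule can count a transfusion-driven Hb as an erythroid response in a patient the SAP keeps in the FAS. The D01 route follows directly from the text; the exit-sample route depends on how SAP 4.2.11 is read.

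The size is 3.3 points on an arm's rate per case. The illustration of 0 to 2 cases around 18/30 v 12/30 is an assumption, since the documents give no transfusion rate; across it, the raw difference runs from 13.3 to 26.7 points. The direction of bias is unknown. No decision rule is tied to the interval in this pilot, so what is at stake is the estimates and how they are read. Confidence is medium, mainly because Module 8 could not be seen. The point should be fixed, because the correction is cheap and better made in advance.

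**What to change.** State in SAP 2.9.1.2 and Protocol 10.4.2:

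- Hb drawn after the first post-randomisation red-cell transfusion cannot establish erythroid response.
- A patient transfused before meeting the criterion is a non-responder and stays in the FAS denominator. A patient who met it before the transfusion remains a responder.

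For transfused patients this settles the result whichever way the End of Treatment window is read. Apply the same rule to the Protocol 6.1.4 statement on Hb reaching 12 g/dL, and to the Hb-based response endpoints in SAP 2.9.2 wherever a transfused patient is in the analysed subset (2.9.2.1 covers only patients who remained in their arm). If RAP Module 8 already holds this rule, cite it in 2.9.1.2.

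Take transfusion dates from the adverse event records (Protocol 8.1.1) and the concomitant therapy records (Protocol 6.4.1). Table 7-1 schedules transfusion history only at Screening 1, Protocol 6.4.1 covers on-study transfusion only by its general wording, and Protocol 8.1.1 asks whether therapy was given without requesting its date. Data queries will therefore be needed where a date is missing.

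The cost is a few sentences, one extra derivation and those queries. Response rates may fall slightly. Clinical management does not change.

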2.9.2 Secondary objectives

The following secondary endpoints will be analyzed by treatment arms.

2.9.2.1 To assess the effect of treatment with DFX+EPO and EPO alone on hematologic response within 24 weeks of treatment

This analysis includes patients who were randomized to EPO and EPO+DFX and remained in their respective treatment arms.

Hematological response will be assessed on this subset of patients and hematological responder is defined as patient meeting at least one of the following modified IWG 2006 criteria:

Hematological response:

- Hb increase from baseline ≥ 1.5 g/dL and Hb < 11 g/dL at baseline (All patients on study per inclusion criterion 5, cf. study protocol section 5.2).
- Neutrophil response: increase from baseline of $\geq 100\%$ and increase $> 0.5 \times 10^9$ /L and neutrophils $< 1.0 \times 10^9$ /L at baseline.
- Platelet response: increase from baseline of $\geq 30 \times 10^9$ /L and platelets $< 100 \times 10^9$ /L at baseline.

Patients who met at least one of the 3 conditions of hematological response at any time between first day of treatment and week 12 or 24 will be considered as responders.

Supportive analyses (proportion of patients, descriptive statistics on the related parameters, change from baseline) will also be provided for patients who do not satisfy the IWG 2006 pre-treatment conditions for neutrophil and/or platelet response (i.e., these patients have baseline neutrophils $\geq 1.0 \times 10^9$ /L and baseline platelets $\geq 100 \times 10^9$ /L) but show hematologic improvement with respect to neutrophils (increase from baseline $> 0.5 \times 10^9$ /L) and/or platelets (increase from baseline $\geq 30 \times 10^9$ /L).

Proportion of patients achieving a hematological response within 12 weeks and within 24 weeks of treatment with DFX combined with EPO and EPO alone will be calculated along with 95% Clopper-Pearson confidence interval. Descriptive statistics will be provided for

hematological improvement response, as well as for all hematological improvement of myeloid cell lineages subcomponents (hemoglobin, erythrocytes, neutrophils and platelets). Analysis will be performed on FAS.

Hematologic response and improvement within 12 weeks and 24 weeks will be analyzed separately.

Table 2-2 summarizes the distinction between response and improvement as being used for supportive analyses:

Table 2-2 Criteria for hematological response and hematologic improvement

	Pre-treatment conditions	Post-baseline	Response
Hematological response: If a patient fulfills at least erythroid or platelet or neutrophil response as well as it's corresponding pre-treatment condition	Hb < 11 g/dL at baseline	Hb increase from baseline by ≥ 1.5 g/dL	Erythroid response
	Platelet < 100×10^9 /L at baseline	Increase from baseline $\geq 30 \times 10^9$ /L	Platelet response
	Neutrophil < 1.0×10^9 /L at baseline	Increase from baseline > 100% and increase from baseline > 0.5×10^9 /L	Neutrophil response
Hematologic improvement: If a patient fulfills at least hemoglobin or platelet or neutrophil improvement response without it's corresponding pre-treatment condition	Hemoglobin < 11 g/dL at baseline	Increase from baseline by ≥ 1 g/dL	Hemoglobin improvement
	Platelet $\geq 100 \times 10^9$ /L at baseline	Increase from baseline $\geq 30 \times 10^9$ /L	Platelet improvement
	Neutrophil $\geq 1.0 \times 10^9$ /L at baseline	Increase from baseline > 0.5×10^9 /L	Neutrophil improvement

2.9.2.2 To assess the effect of treatment on erythropoiesis within 24 weeks in patients who were non-responder to EPO alone after 12 weeks and switched to DFX+EPO

Patients who are non-responders to erythroid at week 12 in the EPO group will have to switch to combination therapy, if they continue to participate in the study.

Patients meeting the criterion (Hb increase from baseline ≥ 1.5 g/dL) at any time between week 12 and week 24 will be considered as erythroid responders.

Proportion of erythroid responders between week 13 and 24 will be reported along with its 95% Clopper-Pearson confidence interval. Descriptive statistics will be provided for erythroid response. Analysis will be performed on FAS.

2.9.2.3 To assess the effect of treatment with EPO alone on erythropoiesis within 24 weeks of treatment

This analysis includes patients who started with the EPO alone and are not switched to combination therapy.

Patients meeting the criterion (Hb increase from baseline ≥ 1.5 g/dL) at any time between week 1 and week 24 will be considered as erythroid responders. Proportion of erythroid responders who starts with EPO alone and are not switched to combination therapy will be reported along with its 95% Clopper-Pearson confidence interval.

Descriptive statistics will be provided for erythroid response. Analysis will be performed on FAS.

2.9.2.4 To assess iron parameters in patients randomized to EPO alone, DFX+EPO and in patients randomized to EPO alone and switched to DFX+EPO after 12 weeks

This analysis will include patients randomized either to EPO or DFX+EPO at baseline as well as patients who are non-responders to erythroid at week 12 in the EPO group switched to combination therapy. The time-course of serum ferritin and its absolute/relative changes from baseline will be summarized by descriptive statistics by visit and erythroid response. Data will be summarized on FAS.

Note: Patients randomized to EPO and not switching after 12 weeks to EPO+DFX, will consist of only responders.

2.9.2.5 To assess Hb parameters in patients randomized to EPO alone, DFX+EPO and in patients randomized to EPO alone and switched to DFX+EPO after 12 weeks

This analysis will include patients randomized either to EPO or DFX+EPO at baseline as well as patients who are non-responders to erythroid at week 12 in the EPO group switched to combination therapy. The time-course of Hb and its absolute/relative changes from baseline will be summarized by descriptive statistics by visit and erythroid response. Data will be summarized on FAS.

Note: Patients randomized to EPO and not switching after 12 weeks to EPO+DFX, will consist of only responders.

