As the EPO guidelines only provide guidance for EPO use (EPO dosing, dose adjustments and dose discontinuation) and do not specify any criteria for the evaluation of erythroid response in MDS patients, in this study, the primary objective erythroid response will be assessed according to IWG criteria (Hb increase ≥ 1.5 g/dL) at 12 weeks of treatment. At any time, if Hb ≥ 12 g/dL, EPO will be stopped until the end of study. Patients treated with the combination therapy will stop EPO if Hb ≥ 12 g/dL and continue on DFX.

At 24 weeks, patients initially assigned to the combination therapy who showed Hb increase ≥ 1 g/dL at week 12 will be assessed for full hematological response according to IWG criteria (Erythroid response: Hb increase from baseline ≥ 1.5 g/dL; Neutrophil response: increase from baseline of $\geq 100\%$ and $> 0.5 \times 10^9/L$; Platelet response: increase from baseline of $\geq 30 \times 10^9/L$).

Patients initially treated with EPO alone and switched to the combination therapy with EPO and DFX after 12 weeks will be assessed for erythroid response at study end after 24 weeks of study treatment.

Figure 4-1 Study Design

Pre-treatment phase (Screening)

At Screening Visit (Visit 1) the investigator or his/her designee will assign a unique number to patients being considered for the study.

Prior to performing any study-related procedures or assessments, the patient must provide written consent to participation in this study. A screening period (up to 28 days) will be used to assess patient eligibility. Two Screening Visits will be required because key safety parameters need to be performed twice before the first dose administration ([Table 7-1](#)).

This study will use an Interactive Web Response (IWR) technology for randomization. Once the patient provides a signed informed consent form and eligibility is confirmed (all inclusion/exclusion criteria have been verified) the investigator and/or his designee can register the patient using the IWR.

Treatment phase

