2.2 Data included in the analyses

Data will be collected on patients aged ≥ 18 years or older with low- and-int-1-risk MDS, randomized in 1:1 ratio to DFX+EPO or EPO alone. If after 12 weeks of treatment with EPO alone, Hb increase is < 1 g/dL and total Hb is < 12 g/dL, the patient will switch to combination therapy of EPO and DFX. The study treatment duration is 24 weeks.

As per the current protocol, no interim analysis is planned. All interim (if required) and final CSRs will have a documented medical review by [REDACTED].

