2.3 Analysis sets

The analysis will consider the following populations:

Full Analysis Set: The Full Analysis Set (FAS) comprises all patients to whom study treatment has been assigned by randomization (EPO or EPO+DFX). According to the intent to treat principle, patients will be analyzed according to the treatment they have been assigned to during the randomization procedure.

Safety Set: The Safety Set includes all randomized patients who received at least one dose of study medication, i.e. either EPO or EPO+DFX, and with at least one post-baseline safety assessment (e.g. lab, vital signs, AEs) and the statement that a subject did not experience an AE can currently be regarded as a valid safety assessment.

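### The secondary EPO-alone response rates drop patients who switched at week 12 for poor Hb response, so they describe a responder-enriched subset labelled FAS, even for the 12-week rate

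*SAP*

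**What the plan says.** SAP 2.9.2.1 (hematological response) opens with the restriction: "This analysis includes patients who were randomized to EPO and EPO+DFX and remained in their respective treatment arms". It then plans the "Proportion of patients achieving a hematological response within 12 weeks and within 24 weeks of treatment with DFX combined with EPO and EPO alone", each with a Clopper-Pearson interval, and names the FAS as the analysis set. Protocol 10.5.1 has the same restriction but plans only the 24-week rate; the 12-week rate is a SAP addition.

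SAP 2.9.2.3 (erythroid response on EPO alone to week 24) is limited in the same way: "This analysis includes patients who started with the EPO alone and are not switched to combination therapy". It also names the FAS. Protocol 10.5.4 matches.

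The switch depends on the outcome. SAP 2.2 sets the trigger: "If after 12 weeks of treatment with EPO alone, Hb increase is < 1 g/dL and total Hb is < 12 g/dL". SAP 2.9.2.2 says: "Patients who are non-responders to erythroid at week 12 in the EPO group will have to switch to combination therapy". In the combination arm the same Hb status leads to discontinuation instead (Protocol Table 4-1, SAP Table 2-1).

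SAP 2.3 defines the analysis set: "The Full Analysis Set (FAS) comprises all patients to whom study treatment has been assigned by randomization (EPO or EPO+DFX"). The primary analysis in SAP 2.9.1.2 uses that set without restriction: "Erythroid response proportion will be also summarized by treatment group with its 95% Clopper-Pearson confidence intervals".

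**The concern.** Patients leave the EPO-alone group because their Hb did not rise enough. A response rate computed among those who stay has lost mainly non-responders from its denominator. The SAP recognises the selection: its notes in 2.9.2.4 and 2.9.2.5 describe the EPO patients who do not switch as responders only. That is slightly too strong. A patient with a rise of 1.0 to under 1.5 g/dL neither switches nor responds, and a patient with an earlier peak of 1.5 g/dL or more can still switch. Responder-enriched is the accurate description.

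Three consequences follow.

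- **Label.** A table headed FAS would not contain all randomised EPO patients, so the rate would not describe the randomised arm.
- **12 weeks.** Every EPO patient is on EPO alone throughout this window. Dropping later switchers uses week-12 information to choose the denominator for the period before it. The erythroid component could then differ from the primary 12-week erythroid rate for the same arm, with both called FAS. A switcher's neutrophil or platelet response in weeks 1 to 12 would enter no hematological response rate.
- **Side-by-side reading.** The plan does not say whether a combination patient discontinued at week 12 counts as having remained. Such a patient never changes arm, which suggests yes. However, Protocol 4.1 says "patients initially assigned to the combination therapy who showed Hb increase ≥ 1 g/dL at week 12 will be assessed for full hematological response" at 24 weeks, and 6.1.4 is similar; this can be read as a matching filter. How the arms look next to each other depends on which reading is used.

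**Working it through.** **Inputs.** About 60 patients randomised 1:1, so 30 per arm (SAP 2.11 and 3.2). Reference response rate 40% (SAP 2.11), so 12 of 30 EPO responders. The number of switchers, s, is not given and is varied.

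**The plan's own figures.** None is stated for these secondary rates. The sample-size intervals in SAP 2.11 do reproduce with 30 per arm if the planning rates are treated as adjusted proportions over n + 2 = 32. For 60% against 40%: 0.20 ± 1.96 × √(0.24/32 + 0.24/32) = (−0.04, 0.44), as stated. This supports 30 per arm as the working size.

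**Step 1: EPO rate under the subset rule, all switchers non-responders.** Rate = 12/(30 − s), with exact 95% intervals:

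| Switchers s | Rate | Clopper-Pearson 95% |
|---|---|---|
| 0 (all randomised) | 12/30 = 40% | 23% to 59% |
| 9 | 12/21 = 57% | 34% to 78% |
| 11 | 12/19 = 63% | 38% to 84% |
| 15 | 12/15 = 80% | 52% to 96% |
| 18 | 12/12 = 100% | 74% to 100% |

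The last row needs every non-responder to switch. At 11 switchers, the 12-week erythroid rate would be 63% in this subset against 40% in the primary analysis.

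**Step 2: some switchers had responded** (an earlier Hb peak, or neutrophils or platelets). With k responders among 11 switchers, rate = (12 − k)/19. For k = 2 it is 10/19 = 53%; for k = 4, 8/19 = 42%; for k = 5, 7/19 = 37%. The inflation shrinks and then disappears.

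**Step 3: reading A, discontinued combination patients stay in the denominator.** The order of the arms reverses when 12/(30 − s) exceeds the true combination rate.

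- True rate 60%: from s = 11 (12/19 = 63%). At s = 9 it does not reverse (57% against 60%).
- True rate 70%: from s = 13 (12/17 = 71%).
- True rate 80%: from s = 16 (12/14 = 86%).

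**Step 4: reading B, both arms lose the same share f of non-responders.** With true rates of 40% and 60%, EPO = 12/(30 − 18f) and combination = 18/(30 − 12f).

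| f | EPO | Combination | Difference |
|---|---|---|---|
| 0.50 | 57% | 75% | 18 points |
| 0.611 | 63% | 79% | 16 points |
| 0.833 | 80% | 90% | 10 points |

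Both rates are inflated and the true 20-point contrast shrinks, but it does not reverse. If the true rates are equal, the difference stays at zero for every f.

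**The case against.** The restriction is disclosed. SAP 2.9.2.1 calls the group a subset, 2.9.2.3 names non-switched patients, and the FAS statement can be read as FAS with a stated restriction. Protocol 10.3 plans to report how many patients switch, SAP 2.9.2.2 reports switchers' later erythroid response, and the primary analysis gives the unrestricted 12-week erythroid rate. A careful reader could see the selection. This is fair, but none of it restores the 24-week EPO-alone rate or the composite hematological rate, and the label still contradicts SAP 2.3.

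The 12-week point can be contested. The SAP says the 12- and 24-week results are analysed separately and does not say until when a patient must have remained. If it means through the window analysed, no later switcher is lost at 12 weeks. On the literal text, one restriction governs the whole section. If the narrower meaning is intended, it has to be written.

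The erythroid component in 2.9.2.1 is promised only descriptive statistics, so the 63% with its exact interval illustrates a possible discrepancy; it is not an explicitly planned output. That stands. So does the point that 40% is a 12-week erythroid planning value, borrowed here for composite and 24-week rates, and that Steps 3 and 4 concern a contrast the plan does not formally make.

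Finally, response to EPO alone after week 12 can be observed only in patients still on EPO alone, so counting switchers as non-responders afterwards is one estimand among several. This is correct, and it is a reason to name the estimand. It gives no support to excluding switchers at 12 weeks.

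**Conclusion.** The concern holds. The EPO-alone denominators in SAP 2.9.2.1 and 2.9.2.3 (Protocol 10.5.1 and 10.5.4) are selected on the outcome and carry a label that the plan's own definition contradicts. On the literal text this extends to the added 12-week rate.

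The direction is upward unless the switchers' own response rate matches or exceeds that of the whole arm. The amount is not knowable from the documents. The illustrated 57% to 100% in place of 40% rests on 30 per arm, the borrowed 40% rate, 9 to 18 assumed switchers and no responders among them.

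This should be fixed but is not critical. The endpoints are secondary and descriptive, no between-arm difference is planned for them, and the primary analysis is untouched. In a pilot whose main product is estimates, a selected control rate presented as FAS could still mislead readers and later planning.

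**What to change.** In SAP 2.9.2.1 and 2.9.2.3 and Protocol 10.5.1 and 10.5.4:

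1. Use all FAS patients by randomised arm as the denominator.
2. Remove the restriction from the 12-week rate.
3. For the 24-week EPO-alone rate, count a switcher as a responder only if the criterion was met on or before the switch, and state this as the chosen estimand.
4. Keep combination patients discontinued at week 12 in their arm's denominator, counted by their status up to discontinuation.
5. Reconcile the 24-week assessment wording in Protocol 4.1 and 6.1.4 with Protocol 10.5.1 and SAP 2.9.2.1, so that one denominator rule is stated for both arms.
6. Show the subset that stayed in its arm only as a supplement, labelled as such, with its n beside the randomised n.

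The cost is wording in two documents and a changed denominator in the tables; the data are already collected. The reported EPO-alone rate will probably be lower than under the current rule, and the text must say that the 24-week convention is one choice among several.
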